RESEARCH PROTOCOL

Version 1.5

Date 10/6/2016

Research Title: Objective, Prospective Measurement of Anterior Chamber Cell Grading Using Anterior Chamber Ocular Coherence Tomography

Short Title: Prospective OCT Measurement of AC Cells

Purpose:

- To determine the feasibility of objective measurement of anterior chamber (AC) cell count utilizing
 - the SPECTRALIS (Heidelberg Engineering, Franklin, MA) spectral domain optical coherence tomography (OCT) system
 - the iSCAN (Optovue, Fremont, CA) spectral domain OCT system
- To develop algorithms that automatically differentiate between cells and “noise” in the anterior chamber OCT (AC-OCT) images and objectively measure the cell density
- To correlate the objective AC cell density measurement and the subjective clinical AC cell grading
- To compare the objective AC cell density measurement with subject treatment outcomes

Introduction:

Treatment decisions for patients with uveitis are currently formulated largely on subjective clinical exam data with high interobserver variation.¹ The most used and most accurate of these subjective clinical data is anterior chamber (AC) cell grade, a measure of intraocular inflammation.¹ AC cell grade is measured by experienced clinicians who manually count the number of leukocytes in a 1mm by 1mm beam of light in the AC visible through a slit lamp stereoscope. The result is a “grade” for AC cells on a nonlinear, ordinal scale as follows: grade 0 is <1 cell, grade 0.5+ is 1-5 cells, grade 1+ is 6-15 cells, grade 2+ is 16-25 cells, grade 3+ is 26-50 cells, and grade 4+ is >50 cells.² The wide range of cells included in the higher grades means that a large change in anterior chamber inflammation might go unnoticed. For example, a patient with 28 cells at their last visit (grade 3+) but 48 cells at their current visit (still grade 3+) would have their 71% increase in intraocular inflammation go unnoticed, as they are still grade 3+. This has concerning implications for both the treatment of patients with intraocular inflammation and the evaluation of interventions that target intraocular inflammation (such as pharmaceuticals).

People with uveitis and people who recently underwent cataract extraction surgery often have intraocular inflammation on clinical exam. Those with uveitis are generally given anti-inflammatory medication to resolve their inflammation. Inflammation after cataract extraction surgery is generally self-resolving.

Optical Coherence Tomography (OCT) uses infrared light with a central wavelength of 840 - 870 nm from a superluminescent diode to scan ocular structures and produce cross sectional and three dimensional images.^{3,4} It is considered a Class 1 laser product that, “does not pose any safety hazard whatsoever.”^{3,5}

RUTGERS APPROVED
THE STATE UNIVERSITY
OF NEW JERSEY

IRB ID: Pro20160000585
Approval Date: 10/24/2016
Expiration Date: 7/19/2017

Title: Prospective OCT Measurement of AC Cells

PI: [name]

OCT machines are used widely in ophthalmology clinics to image the retina and objectively measure glaucoma progression. It can also be used to image the anterior chamber.

A few studies have evaluated the feasibility of imaging the AC to objectively measure intraocular inflammation using optical coherence tomography (OCT). Many of these have used older, time domain OCT (TD-OCT) devices, with resolutions larger than most leukocytes.⁶⁻⁸ One has used newer, spectral domain OCT (SD-OCT) technology with promising results.⁹ No study that we are aware of, however, has either used the SPECTRALIS or iSCAN SD-OCT systems for these measurements, or correlated these measurements against clinical outcomes. We plan to use the SPECTRALIS and iSCAN SD-OCT systems to image the AC of subjects with intraocular inflammation, automate the objective reading of AC cell count from these images, correlate the objective count with the subjective clinical grade, and observe if the correlation is strong enough to guide treatment decisions.

Hypothesis:

Automated, objective measurement of anterior chamber cell count with the SPECTRALIS (Heidelberg Engineering, Franklin, MA) and iSCAN (Optovue, Fremont, CA) spectral domain optical coherence tomography systems cannot be used to guide the treatment of patients with intraocular inflammation.

Methods:

This is a prospective clinical imaging study. Treatment and follow up of subjects will not be altered through this study. Subjects will be selected from the pool of patients in the Doctors Office Center (DOC) at New Jersey Medical School/University Hospital who attend the Wednesday Uveitis clinic. The clinic is staffed by two staff physicians ([name] and [name]) and a rotating staff of NJMS ophthalmology residents. Non-patient control subjects may also have an opportunity to participate in this study; this group will include friends and relatives of enrolled subjects and any person who volunteers for the study (such as those who saw the study registered on clinicaltrials.gov). Up to 300 subjects will be enrolled.

Three groups of subjects will be enrolled: one “uveitis imaging” group, one “cataract imaging” group, and one “control” group. The uveitis imaging group will include subjects with uveitis. The cataract imaging group will include subjects who have just undergone cataract extraction surgery within the previous 30 days. The third group will function as a control. Inclusion criteria for both imaging groups will include an age over 18 years old and active anterior chamber inflammation in at least one eye as diagnosed by clinical exam. Inclusion criteria for the uveitis imaging group will also include a diagnosis of uveitis. Inclusion criteria for the cataract imaging group will also include having recently undergone cataract extraction surgery within the previous 30 days. Inclusion criteria for controls will include an age of 18 years old in subjects with and without uveitis who do not have active intraocular inflammation based on clinical exam. Exclusion criteria for all three groups will include corneal opacities in the affected eye that would limit objective measurement by OCT and anyone judged unable to understand or consent to study participation. The two staff physicians will identify eligible subjects for inclusion. Controls will be recruited from the same clinic described above. Controls will include patients who meet the inclusion criteria above, and also non-patient control subjects who meet the inclusion criteria above.

RUTGERS APPROVED
2

Title: Prospective OCT Measurement of AC Cells

PI: [name]

Prior to the scan, non-patient control subjects will also undergo a brief, non-contact ocular exam by either [name] or [name], to ensure that they meet inclusion and do not meet exclusion criteria (e.g. they have no intraocular inflammation and no corneal opacities); this exam will not require any eye drops.

The study will be thoroughly explained to any potential subjects identified by the two staff physicians. Subjects recruited will be patients of the investigators or non-patient control subjects (such as the relatives and friends of those patients who attend the clinic with them). Any potential subject will be asked to participate and will have the study thoroughly explained to them. They will have the opportunity to ask questions and will be given ample time to decide on participation or nonparticipation. They will also have the opportunity to discuss the study and their participation with relatives or friends. They will be notified that their participation is completely optional and that participation or nonparticipation in this study will not alter or affect their relationship with their doctor or any of their healthcare providers. To avoid coercion, the study risks will be carefully explained to subjects and it will be emphasized that participation is completely optional and not required for their medical care or for their relationship with their physician. A subject's participation or nonparticipation in this study will not alter or affect their medical care in any way. Treatment of subject's uveitis will still be based on clinical examination, and not on any information obtained from the OCT imaging. The consent process will be administered by any of the following study staff ("study personnel obtaining consent"): [name], study coordinator and NJMS medical student; [name] and uveitis specialist; and [name] and uveitis specialist.

The study personnel obtaining consent will ensure each subject has verbal fluency of the English language and is well able to understand the study procedures and consent form. People of all economic classes and educational levels will be invited equally to participate in the study. Minority status will also not be a factor in participation. Children, prisoners, and pregnant woman will not be included in this study. Pregnant woman will not be included due to the majority of expected eligible patients being non-pregnant.

The study personnel obtaining consent will assess capacity. Only subjects who have capacity to consent will be allowed to participate. The study personnel obtaining consent will also assess subjects' comprehension of the study. Only subjects who fully comprehend their role in the study will be allowed to participate. Subjects who do not understand their role and the risks and benefits will be ineligible to participate. This includes subjects with significant cognitive impairments and who do not speak English. Subjects with hearing impairments will be allowed to participate as long as they can understand their role in the study and understand explanations from the study personnel obtaining consent. Subject's continued capacity for consent will be monitored by the study personnel who obtain consent. They will be reminded before each image acquisition that they do not have to participate and that they can drop out of the study whenever they want to. The principal investigator may discontinue the study with any subjects who are unfit to participate.

The OCT scan will be taken by either the SPECTRALIS or iSCAN OCT systems, or both. The SPECTRALIS is owned by Rutgers University, and it is stored in a locked room in DOC 6136. The iSCAN is owned by

Title: Prospective OCT Measurement of AC Cells

PI: [name]

Rutgers University, and it is stored in a locked room in DOC 6100A. The image for both OCT systems will be taken by [name], the study coordinator and NJMS medical student, who has extensive experience operating various OCT machines and has been trained in operating the SPECTRALIS and iSCAN.

Subjects who meet inclusion criteria, do not meet exclusion criteria, and who agree to participate in the study will be asked to sign a consent form. Non-patient control subjects will then be given a non-contact ophthalmic exam by either [name] or [name]. All subjects will then be taken to one of two OCT imaging rooms (DOC 6136 or DOC 6100A), where the process of imaging will be explained and carried out. The scan itself will take less than one minute. After consent is obtained, the entire imaging process will take approximately 10-20 minutes. The consent and imaging process will occur at the end of the subject's normal exam visit. The consent, exam, and imaging process for non-patient control subjects will occur at pre-scheduled times arranged individually by the subjects and study staff.

Choice of which OCT system to use (SPECTRALIS or iSCAN) will depend on OCT and subject availability. Subjects will generally be asked to use the SPECTRALIS OCT system. If the SPECTRALIS is being used for clinic patients, subjects will be asked to instead use the iSCAN system. If they have time and agree, some subjects will be asked to use both systems to ensure similar results can be obtained from each system. The system used on a subject's first visit will determine which system they use for their entire enrollment. Subjects will use the same OCT system for the duration of their enrollment in this study.

Each enrolled subject will be scanned a total of between one and eight times over a period of two to eight weeks, depending on the dates of their scheduled follow up visits in clinic. The scans will only occur on their regularly scheduled clinic visits. The first scan will occur on the first visit where they are identified as eligible and they agree to participate. Patients with active intraocular inflammation in the uveitis clinic are generally prescribed anti-inflammatory medications and asked to return within a few days to weeks to evaluate resolution of the inflammation. Patients who recently underwent cataract extraction surgery are also asked to return within a few days to weeks to follow up the surgery. On these follow up visits, the subjects will be reminded that participation is optional and they will be asked to undergo another OCT scan. Subjects who agree will be scanned again on these follow up visits with the same procedure described above. This will allow us to identify both inflammation and resolution of inflammation on the study images and analyze the data as described in the last paragraph of this protocol. Non-patient control subjects will have the option of only undergoing one scan or individually scheduling follow-up visits for repeat scans for up to eight total scans over a period of two to eight weeks. No subject will be scanned more than eight times in total for this study.

The scans performed by the SPECTRALIS and iSCAN OCT machines are non-contact procedures that use safe, infrared light. The subject rests their chin and forehead into plastic rests that are cleaned with alcohol between each use. The SPECTRALIS or iSCAN OCT can then image the subject's eye. The subject's eye will not be touched for this scan or for any part of this study. No eye drops will be used for this study, as none are required for these high quality, non-contact scans.

Title: Prospective OCT Measurement of AC Cells

PI: [name]

All study activities will be performed in the Doctor's Office Center suite 6100. Subject recruitment and the consent process will occur in exam rooms owned by Rutgers University in DOC 6100. Subjects who enroll in the study, as described above, will be brought to either DOC 6136 or DOC 6100A, where the SPECTRALIS OCT or iSCAN OCT, respectively, are stored and where the study scans will be performed; this room and the equipment are owned by Rutgers University. Data storage and analysis will take place on computers and in locked areas of DOC 6100 owned by Rutgers University.

A list of participating subjects with unique identification keys will be kept in the locked room of a secondarily locked research area by the study coordinator.

Data taken from the medical record will include: name, date of birth, medical record number, inflammation status, and ocular history. The name, date of birth, and medical record number will be used to coordinate scans for subject's follow-up visits. The inflammation status and ocular history will be used to make appropriate comparisons for the study.

Scan data will be stored in the SPECTRALIS or iSCAN OCT systems as is standard for clinical practice. Scan data will be taken from the OCT system via encrypted USB drive upon each subject's completion in the study. The data will then be de-identified, labeled with the unique identification key described above, and stored in the locked room of a secondarily locked research area. The key will remain on paper in a locked room in a secondarily locked research area in the DOC. Only the study coordinator and principle investigator will have access to the data.

Subject risks include potential breach of confidentiality of information collected and the loss of 10-20 minutes of time required to complete the OCT scan process. The risk of breach of confidentiality of information is minimal due to the lack of collection of sensitive information and will be further minimized by storing data in locked and password protected files, as described above. Subject benefits include potentially increased understanding of intraocular inflammation and the new management standards that may be applied to their, and others', uveitis treatment in the future.

All subject data obtained will be confidential. Data will only be released in aggregate and no subjects' personal identifiers will be revealed.

De-identified image data from the SPECTRALIS and iSCAN OCT systems will be analyzed two ways. The first analysis methodology will be the manual identification of leukocytes on the OCT image by the staff uveitis specialists. The second analysis methodology will be the automatic identification of leukocytes on the OCT image by computer algorithm. The AC cell count results of the two analysis methodologies will be compared to subject's clinical AC cell grading. Statistical analysis using T-test and other statistical tools will be used to compare the study and the clinical AC cell count methodologies. Study AC cell count results will also be correlated with the actual subject treatment plans and outcomes to test the null hypothesis that the study results would not have been able to correctly guide subject treatment decisions.

References:

Title: Prospective OCT Measurement of AC Cells

PI: [name]

3. *User Manual: SPECTRALIS HRA+OCT.* Heidelberg Engineering GmbH;2012.
4. ISCAN. *Optovue* 2016; <http://www.optovue.com/products/iscan/>, 2016.
5. Laser Safety Information. *Laser Institute of America* 2016; https://www.lia.org/subscriptions/safety_bulletin/laser_safety_information. Accessed March 31, 2016.

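### Unequal repeat scans, some on two OCT systems, go to an analysis that names only a T-test and an unspecified correlation, with no rule for unit, pairing or within-subject correlation

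*Combined protocol and SAP*

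**What the plan says.** The scan-schedule paragraph of Methods reads: "Each enrolled subject will be scanned a total of between one and eight times over a period of two to eight weeks". The number depends on clinic follow-up dates and continued agreement, with a cap of eight. Scan counts will therefore be unequal, and for one group a single scan is explicitly allowed: "Non-patient control subjects will have the option of only undergoing one scan". Follow-up scans are intended analysis data, because their purpose is to show inflammation and "resolution of inflammation on the study images and analyze the data as described in the last paragraph of this protocol".

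On the imaging systems, Methods says that "some subjects will be asked to use both systems to ensure similar results can be obtained from each system". It also says that the system used at the first visit "will determine which system they use for their entire enrollment", and then that one system is kept throughout. On eyes, the inclusion criteria accept inflammation in one or both eyes, while the exclusion criteria speak of a single affected eye.

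The last paragraph of Methods is the whole analysis plan. Manual and automated OCT counts are each set against the clinical grade: "Statistical analysis using T-test and other statistical tools will be used to compare the study and the clinical AC cell count methodologies". Counts are also correlated with treatment plans and outcomes "to test the null hypothesis that the study results would not have been able to correctly guide subject treatment decisions". The Introduction describes the grade as ordinal and nonlinear, and says that the study will "observe if the correlation is strong enough to guide treatment decisions".

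**The concern.** A plain T-test or a simple correlation treats each observation as independent. Here one subject may supply up to eight scans. A single visit may yield two OCT counts, one per system, against one clinical grade, and two eyes may add a further layer. The plan does not say whether the scan, eye, visit or subject is the unit. It does not say whether the T-test is paired, or how repeat and two-system scans enter.

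A second problem concerns scale. A T-test of an OCT count against a clinical grade compares a cell count with an ordinal code, and a difference of zero between the two means nothing.

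What is at stake is how the result is read. The study tests a stated null hypothesis and asks whether a correlation is strong enough to act on, so overstated precision bears directly on its conclusion. Methods states that treatment is not altered by the study, so no harm to subjects follows.

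**Working it through.** **Inputs from the protocol.** Scans per subject: 1 to 8. Enrolment: up to 300, a ceiling with no derivation. No alpha, power, effect size, standard deviation, intraclass correlation (ICC) or scan distribution is given, so there is no stated figure to reproduce.

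**Assumptions, for illustration only.** All scans are pooled; the level is nominal two-sided 5%; ICC is 0.1 to 0.7; scan counts are spread evenly over 1-4 or 1-8; there is one system per visit unless stated.

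**Step 1: cluster-size ratio.** k = Σm²/Σm. For 1-4 scans, 30/10 = 3.00. For 1-8 scans, 204/36 = 5.67.

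**Step 2: pooled correlation.** The true correlation is set at 0.7 both between and within subjects, both measures have the same ICC, and there are 300 subjects and 4,000 runs. Simulated coverage of the nominal 95% Fisher-z interval:

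| ICC | 1-4 scans | 1-8 scans |
|---|---|---|
| 0 | 0.951 | 0.954 |
| 0.1 | 0.950 | 0.942 |
| 0.3 | 0.930 | 0.907 |
| 0.5 | 0.890 | 0.812 |
| 0.7 | 0.835 | 0.713 |

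Check by formula: DE = 1 + (k - 1) × ICC², and coverage = 2Φ(1.96/√DE) - 1. At ICC 0.7, DE = 1 + 2 × 0.49 = 1.98 gives 0.836, and DE = 1 + 4.67 × 0.49 = 3.29 gives 0.720. The mean estimate stays at 0.70 in this set-up.

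**Step 3: same-scale paired T-test**, such as manual minus automated count, where the ICC is that of the differences. DE = 1 + (k - 1) × ICC, and actual error = 2[1 - Φ(1.96/√DE)].

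| ICC | DE, 1-4 | Error, 1-4 | DE, 1-8 | Error, 1-8 |
|---|---|---|---|---|
| 0.1 | 1.20 | 0.074 | 1.47 | 0.106 |
| 0.3 | 1.60 | 0.121 | 2.40 | 0.206 |
| 0.5 | 2.00 | 0.166 | 3.33 | 0.283 |
| 0.7 | 2.40 | 0.206 | 4.27 | 0.343 |

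Simulation with 300 subjects gave 0.068 to 0.203 (1-4 scans) and 0.111 to 0.345 (1-8 scans).

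**Step 4: pairing ignored.** An unpaired T-test of two methods on the same scans (1-8 scans, ICC of the differences 0.1 to 0.7) had a simulated error of 2% to 19% at an assumed between-method correlation of 0.5, and 0.3% to 9% at 0.7. The error can therefore go either way.

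**Step 5: two systems.** Suppose 25% of subjects are scanned on both systems at each of 1-4 visits (within the cap of eight), with between-system correlation 0.9 and everything pooled. Coverage for the correlation is then 91% at ICC 0, and 91% to 79% over ICC 0.1 to 0.7. The 25% and the 0.9 are assumptions.

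**The case against.** The strongest reply is that the plan never says scans will be pooled. Its unnamed further tools could include a mixed model, and its T-test could be a paired one. That stands. A reader might infer that the study will treat repeat scans as independent, or that its error rate will be 34%; the documents support neither. The highest error rates, in step 3, belong to a same-scale difference that the last paragraph of Methods does not name, since it sets both OCT counts against the clinical grade.

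It is also fair that high ICCs are unsupported. Inflammation is expected to resolve between visits, which adds within-subject variation. An even spread up to eight scans within eight weeks implies near-weekly attendance at a weekly clinic. At ICC 0.1 the correlation interval loses almost nothing. The finding that pooling leaves the estimate at 0.70 holds only for equal between- and within-subject correlation and scan counts unrelated to inflammation.

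Same-visit pairs do exist for patients, because Methods places imaging at the end of the exam visit. Only the analysis rule is absent. The stated purpose of the two-system scans is to check similarity, so pooling them should not be presumed.

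What remains is that no unit, pairing rule or within-subject method appears anywhere, and the one test named needs independent observations on a common scale.

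**Conclusion.** The point holds as a gap in specification that should be closed before analysis. Repeat, unequal and sometimes two-system scans are routed to an analysis whose only named test does not suit them. Should that test or a simple correlation be run over all scans, precision would be misstated whenever scans of one subject are correlated. Nominal 95% coverage for a correlation of 0.7 would be about 95% to 84% (1-4 scans) or 94% to 71% (1-8 scans) over ICC 0.1 to 0.7. A same-scale paired T-test, if one were added, would have an error of 7% to 21% or 11% to 34%. Every one of these figures rests on assumed pooling, ICC and scan distribution. With one scan per subject and one system, or with ICC 0 and one system, there is no such effect. The mismatch between count and ordinal grade does not depend on those assumptions.

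**What to change.** Amend the last paragraph of Methods as follows.

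- **Unit and pairing.** The unit is the eye-visit. Each OCT count, manual and automated analysed separately, is paired with the same eye's clinical grade at that visit.
- **Main model.** Relate count to grade (categorical) in a mixed model with a fixed effect for OCT system and random intercepts for subject and for eye within subject. Fix the count scale (raw or log(count + 1)) in advance.
- **Correlation with grade.** Report Spearman's coefficient with a subject-level cluster bootstrap 95% interval.
- **Stated null hypothesis.** Keep the correlation of counts with treatment plans and outcomes, and apply the same subject-level clustering to it.
- **Same-scale differences.** Manual minus automated, or between systems, use the same random effects in place of a plain T-test.
- **Systems and eyes.** Use one pre-stated system per subject in the main analysis and keep second-system scans for the between-system comparison. For example, use the first-visit system, and every imaged eye that met its group's entry criteria at the first scan. Any rule fixed before the data are seen will do. Reconcile the statements in Methods on using both systems and on keeping one throughout.

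The cost is a few sentences, slightly more analysis work and wider intervals, with no new data or visits. For a correlation of 0.7 with 300 subjects at ICC 0.7, mean interval width goes from 0.073 to 0.101 (1-4 scans) or from 0.054 to 0.097 (1-8 scans); at ICC 0.1 it barely changes. Simpler versions performed well in simulation over ICC 0.1 to 0.7: a random-intercept test of a mean difference had an error of 4.6% to 5.8%, and a cluster bootstrap of Pearson's coefficient covered 93% to 95%. The full mixed model and the Spearman bootstrap have not been simulated.

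### Masking of the manual OCT readers to clinical grade, group and visit order is not specified, so the manual-versus-clinical comparison is at risk of inflated agreement

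*Combined protocol and SAP*

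**What the plan says.** All of the relevant text is in the Methods section of the combined protocol and SAP.

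- **Readers.** The analysis paragraph at the end of Methods defines the first analysis as "the manual identification of leukocytes on the OCT image by the staff uveitis specialists". The second is an automated count. Each is compared with the clinical cell grade, using a T-test and other tools that are not named.
- **Clinic staff.** "The clinic is staffed by two staff physicians", with rotating residents.
- **Selection and group.** "The two staff physicians will identify eligible subjects for inclusion". Both imaging groups require "active anterior chamber inflammation in at least one eye as diagnosed by clinical exam"; controls must have no active inflammation on clinical exam.
- **Consent.** "The consent process will be administered by any of the following study staff", and two of those listed are described as uveitis specialists.
- **Image handling.** "Scan data will be taken from the OCT system via encrypted USB drive upon each" subject completes the study. The images are then de-identified and "labeled with the unique identification key described above". That key comes from a list of participating subjects, which the coordinator keeps in a locked room.
- **Access.** "Only the study coordinator and principle investigator will have access to the data".
- **Repeat scans.** Each subject has one to eight scans over two to eight weeks, timed to capture both inflammation and its resolution.

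**The concern.** The Introduction criticises the clinical grade as subjective, with high variation between observers. A manual count on the OCT image is useful as a check on that grade only if it is made without knowledge of it. A reader who remembers the eye, knows the subject's group, or sees that a set of scans runs from inflamed to quiet has an expectation of what the count should be. If that expectation moves the count toward the grade, the reported agreement is partly the grade agreeing with itself.

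The manual-versus-clinical comparison is what is at stake. The manual count's correlation with treatment plans might also be touched, because the protocol says that treatment continues to rest on clinical examination.

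**Working it through.** **Step 1: the text side by side.** The plan gives no figure on masking. Its only sample-size number is a cap of 300 subjects, which does not bear on this point. The check is therefore mainly one of reading.

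| Question | What Methods states | What it leaves open |
|---|---|---|
| Who reads manually? | Staff uveitis specialists | Whether a specialist may read an eye that he or she examined |
| Who records the clinical grade? | Not stated; two staff physicians and residents staff the clinic | The grader at each visit |
| Is identity masked? | In part: de-identified images, locked key list, export at subject completion | Whether images shown to readers carry scan dates |
| Are a subject's scans linkable? | Yes: one key per subject, and no code per scan is described | Whether readers receive scans as sets or in visit order |
| Are readers masked to grade, group or visit order? | Not stated | All three |
| Who may see the data? | Coordinator and principal investigator only | How the staff specialists obtain the images they must read |

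Taking the staff physicians and the staff uveitis specialists to be the same people is a natural reading, but names are removed in the public copy. What follows from the text is that a specialist *may* read an eye that he or she examined, and that no rule prevents it.

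**Step 2: size of a pull toward the grade (illustration only).** Let M be the masked manual read and G the clinical grade, both with unit variance and with correlation r. Suppose the unmasked read is M′ = (1−w)M + wG, where w is the fraction of the way that the reader moves toward the grade. Then

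corr(M′, G) = [(1−w)r + w] / √[(1−w)² + w² + 2w(1−w)r].

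With r = 0.50:

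- w = 0.1: 0.55 / √0.91 = 0.577
- w = 0.2: 0.60 / √0.84 = 0.655
- w = 0.3: 0.65 / √0.79 = 0.731

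For other assumed values of r:

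| r | w = 0 | w = 0.1 | w = 0.2 | w = 0.3 |
|---|---|---|---|---|
| 0.3 | 0.300 | 0.396 | 0.499 | 0.607 |
| 0.5 | 0.500 | 0.577 | 0.655 | 0.731 |
| 0.7 | 0.700 | 0.751 | 0.799 | 0.845 |

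Both r and w are assumptions. At w = 0 there is no inflation.

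**Step 3: a reader who knows only the group.** Let s be the share of variance in the grade that group explains, and let M depend on group only through G. A pull of w toward the group value then gives, for r = 0.50:

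- s = 0.3: 0.541, 0.582 and 0.617 at w = 0.1, 0.2 and 0.3
- s = 0.6: 0.559, 0.619 and 0.676

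The inflation is smaller than in Step 2 but does not vanish.

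**Step 4: the T-test.** On a common scale, M′ − G = (1−w)(M − G), so the mean difference is multiplied by 1−w. At w = 0.3, 70% of it remains. The effect on the test statistic depends on its form, which the plan does not give. In a paired test under this exact model, the standard deviation of the difference shrinks by the same factor and the statistic is unchanged. In an unpaired test with r = 0.50 and w = 0.3, the statistic is multiplied by 0.7 / √[(0.79 + 1)/2] = 0.74.

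**The case against.** The strongest reply is that the plan already separates reader from patient to a useful degree. Images are de-identified before analysis, the key list is locked away with the coordinator, and export waits until the subject has finished, so time passes between exam and read. A subject key is not said to encode group, visit or grade. A general tendency toward resolution does not reveal the grade at any one visit. For clinic patients, imaging follows the exam, so that visit's scan is unlikely to influence that visit's grade. All of this stands. It makes the masking partial rather than absent, and it probably weakens recall.

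Three stronger readings are tempting, and the documents support none of them.

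- A reader might infer that the people who grade the eyes are the people who count the cells, and that the comparison is biased upward as a matter of fact. The grader is not named, residents also staff the clinic, and the pull w cannot be estimated from the documents.
- A reader might infer that the automated count inherits a biased comparator. The analysis paragraph compares each method with the clinical grade. It does not make the manual count the reference or the training data for the algorithm, and the stated hypothesis concerns automated measurement.
- A reader might infer that the principal investigator reads images with the grades in hand. The access rule would permit this only if the principal investigator is a reader, which cannot be established with names removed.

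What the reply does not answer is that de-identification is written as a confidentiality step. No sentence keeps grade, group or visit order from readers, and none stops a specialist reading his or her own patient's eye.

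**Conclusion.** The concern holds as a gap in the plan, not as a demonstrated bias. Masking of the manual readers is neither specified nor assured, and the per-subject label leaves repeat scans linkable. The likely direction is inflated agreement: a higher correlation, or a smaller mean difference where a T-test is used. The 0.58 to 0.73 range for a true 0.50 rests wholly on an assumed pull of 10% to 30% toward the grade. The risk is confined to the manual count. The access rule and the reading plan also conflict as written, since staff specialists must read images that only the coordinator and principal investigator may access. The change is worth making because it protects a planned comparison at little cost.

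**What to change.** In the data-handling and analysis paragraphs of Methods:

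1. The coordinator gives each image its own random code, removes dates, and mixes images across subjects, groups and visits in random order before reading. The coordinator keeps the link back to the subject key.
2. Record who graded each eye at each visit. Each image is read by the staff specialist who did not grade that eye at that visit. This also deals with recall, which withholding records cannot.
3. Readers do not receive the key list or the recorded grades until the reads are locked. This includes the principal investigator if he or she is a reader.
4. Reconcile the data-access rule with the reading plan, so that the staff specialists may see the coded images.

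The cost is protocol wording, a grader field, and some extra file handling by the coordinator. The downside is that reading waits until a batch of subjects has accumulated. No extra reader or procedure is needed.
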